### 9.2.2 Reactogenicity

Not applicable.

### 9.2.3 Serious Adverse Events

**Serious Adverse Event (SAE):** An adverse event or suspected adverse reaction is considered “serious” if it results in any of the following outcomes:

- Death,
- a life-threatening adverse event\*,
- inpatient hospitalization or prolongation of existing hospitalization,
- a persistent or significant incapacity or substantial disruption of the ability to conduct normal life functions, or
- a congenital anomaly/birth defect.
- Important medical events that may not result in death, be life threatening, or require hospitalizations may be considered serious when, based upon appropriate medical judgment they may jeopardize the patient or subject and may require medical or surgical intervention to prevent one of the outcomes listed in this definition. Examples of such medical events include allergic bronchospasm requiring intensive treatment in an emergency room or at home, blood dyscrasias or convulsions that do not result in inpatient hospitalization, or the development of drug dependency or drug abuse.

\* Life-threatening adverse event. An adverse event is considered “life-threatening” if, in the view of either the site principal investigator or sponsor, its occurrence places the patient or subject at immediate risk of death. It does not include an adverse event that, had it occurred in a more severe form, might have caused death.

All SAEs will be:

- Assessed for severity and relationship to study product and alternate etiology (if not related to study product) by a licensed study physician listed on the Form FDA 1572 as the site principal investigator or appropriate sub-investigator.
- Recorded on the appropriate SAE form and eCRF
- Followed through resolution by a licensed study physician listed on the Form FDA 1572 as the site principal investigator or sub-investigator.
- Reviewed and evaluated by the Independent Safety Monitor (ISM), Data and Safety Monitoring Board (DSMB), DMID, and the Institutional Review Board (IRB).

#### **9.2.4 Procedures to be Followed in the Event of Abnormal Laboratory Test Values or Abnormal Clinical Findings**

NP specimens will be obtained for culture at baseline and follow-up for the identification of *S. pneumoniae*, *H. influenzae*, and *M. catarrhalis*. Detection of *S. pneumoniae*, *H. influenzae*, and *M. catarrhalis* in the nasopharynx will be considered a normal finding.

Study product may need to be discontinued in subjects with a clinical adverse event, laboratory abnormality, intercurrent illness, or other medical condition such that continuation of study product would not be in their best interest. Randomization codes will not be broken at any time in the event of treatment failure unless deemed necessary for medical /emergency/safety reasons. These subjects will be asked to continue to record their symptoms on the PRSS on a daily basis and to return to the clinic for a routine end-of-study follow-up visit to be held once during Days 12 to 18.

### **9.3 Reporting Procedures**

Non-serious AEs occurring throughout the study-reporting period will be documented from the first study intervention, Day 1 (enrollment), through the end-of-study follow-up visit (Day 12-18) using the eCRF.

SAEs occurring throughout the study-reporting period will be documented from the first study intervention, Day 1 (enrollment), through the end-of-study follow-up visit (Day 12-18) using the appropriate SAE form and eCRF.

SAEs related to the study product will be reported to the principal investigators and IRBs immediately (within 24 hours of site awareness). Unexpected severe adverse reactions related to study product will be reported to the IRBs per local IRB guidelines and subsequently reported to the principal investigators. Line-item reports of all SAEs and a report of all recorded AEs will be submitted to the DSMB and DMID according to the frequency established in the DSMB charter.

#### **9.3.1 Serious Adverse Events**

Any AE that meets a protocol-defined serious criterion will be submitted immediately (within 24 hours of site awareness) on a SAE form to the DMID Pharmacovigilance Group, at the following address:

DMID Pharmacovigilance Group  
Clinical Research Operations and Management Support (CROMS)  
[name]  
[name]  
SAE Hot Line: [name] (US)  
SAE FAX [contact] (US)  
SAE Email Address: [[contact]](mailto:[contact])

In addition to the SAE form, selected SAE data fields must also be entered into the central database. Other supporting documentation of the event may be requested by the DMID Pharmacovigilance Group and should be provided as soon as possible.

The site will send a copy of the SAE report(s) to the ISM when they are provided to the DMID Pharmacovigilance Group. The DMID medical monitor and clinical protocol manager will be notified of the SAE by the DMID Pharmacovigilance Group. The DMID medical monitor will review and assess the SAE for regulatory reporting and potential impact on study subject safety and protocol conduct.

At any time after completion of the trial, if the investigator becomes aware of an SAE that is suspected to be related to study product, the investigator will report the event to the DMID Pharmacovigilance Group.

### **9.3.2 Regulatory Reporting for Studies Conducted Under IND**

In consultation with DMID, the principal investigators will report any suspected adverse reaction that is both serious and unexpected. The principal investigators will report an adverse event as a suspected adverse reaction only if there is evidence to suggest a causal relationship between the drug and the adverse event. The principal investigators will notify FDA and all participating site principal investigators (i.e., all principal investigators to whom the sponsor is providing drug under its IND(s) or under any principal investigator's IND(s)) in an IND safety report of potential serious risks from clinical trials or any other source, as soon as possible, but in no case later than 15 calendar days after the sponsor determines that the information qualifies for reporting as specified in 21 CFR Part 312.32. The principal investigators will also notify FDA of any unexpected fatal or life-threatening suspected adverse reaction as soon as possible, but in no case later than 7 calendar days after the sponsor's initial receipt of the information. Relevant follow up information to an IND safety report will be submitted as soon as the information is available. Upon request from FDA, the principal investigators will submit to FDA any additional data or information that the agency deems necessary, as soon as possible, but in no case later than 15 calendar days after receiving the request. All serious events designated as "not related" to study product, will be reported to the FDA at least annually in a summary format.

### **9.3.3 Reporting of Pregnancy**

Not applicable.

## 9.4 Type and Duration of Follow-up of Subjects after Adverse Events

AEs will be collected, assessed, and followed through resolution throughout the study-reporting period.

SAEs will be collected, assessed, and followed through resolution even if this extends beyond the study-reporting period.

Resolution of an AE/SAE is defined as the return to pretreatment status or stabilization of the condition with the expectation that it will remain chronic.

Follow-up procedures, evaluations, and outcomes will be recorded on the appropriate form and/or eCRF.

## 9.5 Halting Rules

Further enrollment and study product administration will be halted for DSMB review/recommendation if any of the following are reported:

- Any death occurs following study product administration that was not the result of trauma or accident.
- Any subject develops brain abscess or bacterial meningitis.
- Two subjects develop complications of sinusitis (e.g., orbital cellulitis, frontal bone subperiosteal abscess).

If any of the halting rules are met following any subject receipt of study product, the trial will not proceed with the remaining enrollments or study product administration without a review by and recommendation from the DSMB to proceed. The University of Pittsburgh, IRBs and DMID retain the authority to suspend enrollment and/or study product administration during the entire trial, as applicable.

## 9.6 Safety Oversight (ISM plus DSMB)

Safety oversight will be conducted by an external DSMB, which is an independent group of experts that reviews study data, monitors subject safety and advises DMID and the principal investigators. The DSMB will consist of at least three voting members with appropriate expertise to contribute to the interpretation of the data from this trial including a biostatistician experienced in statistical methods for clinical trials and a clinician with relevant expertise.

The DSMB members will be separate and independent of study personnel participating in this trial and should not have scientific, financial or other conflict of interest related to this trial. To avoid any appearance of conflict of interest, it is critical that DSMB members not be involved in the study, have no vested interest in its outcome, have no ties to the study investigators and have no financial ties to any commercial concerns likely to be affected by the study's outcome.

The DSMB will review study progress and participant, clinical, efficacy, laboratory, and safety data at the following time points:

- At specified times during the course of this trial as defined in the DSMB Charter.
- At the time of the interim analysis (conducted after 344 subjects have been enrolled and completed follow-up).
- Ad hoc when a halting rule is met, for immediate concerns regarding observations during this trial, or as needed.

The DSMB will meet regularly to monitor the cumulative safety data during the period when participants are receiving study product and during the participant follow-up period. The DSMB will monitor the study according to the guidelines specified in the study protocol and the charter established at their initial meeting, unless the DSMB determines during the course of the trial that modification of the guidelines is in the best interest of this trial and its participants. Such a decision may be based on new information that emerges during the course of this trial (e.g., publication of the results of a similar trial), realization of inappropriate initial study assumptions, or the occurrence of an unanticipated scenario.

The DSMB will operate under the rules of a DMID-approved charter that will be written at the organizational meeting of the DSMB. At this time, each data element that the DSMB needs to assess will be clearly defined. Procedures for DSMB reviews and meetings will be defined in the charter. Procedural issues include: the board's meeting frequency; the types and formats of reports it will receive from the DMSU, the policy on whether and how the members may be unblinded; what interim data (if any) may be released to the study investigators (e.g., overall AE rate); and how minutes will be taken and distributed.

Before initiation of this trial, the DSMB will review the study protocol (particularly the specific outcome definitions), halting rules, the interim and final analysis plan, the procedures for recording and reporting SAEs, and the data and safety monitoring plan (including draft shells of safety reports and tables). The informed consent document/process also will be inspected to ensure that all required elements have been included in language understandable to parents/legal guardians of children to be enrolled in this trial.

Study data will be reviewed by the DSMB per the charter for this study. The DSMB will review applicable data to include but not limited to study progress, enrollment, demographic, clinical, efficacy outcomes, laboratory and safety data which includes AE/SAEs, medical history, physical assessments, concomitant medications, compliance, and laboratory results (NP cultures). Interim statistical reports will be generated when 50% of patients have completed the study. Comparative results are presented to the DSMB in closed sessions attended only by voting members of the DSMB and by a representative of DMID. Additional data may be requested by the DSMB, and additional interim statistical reports may be generated as deemed necessary and appropriate by DMID. The DSMB may receive data in aggregate and presented by group. The DSMB may also be provided with expected and observed rates of the expected AEs in an unblinded fashion, and may request treatment assignment be unblinded for an individual subject if required for safety assessment. The DSMB will review grouped and unblinded data in the closed session only. As an outcome of each review or meeting, the DSMB

will make a recommendation as to the advisability of proceeding with enrollment and study product administration (as applicable), and to continue, modify, or terminate this trial.

DMID or the DSMB chair may convene the DSMB on an ad hoc basis according to protocol criteria or if there are immediate concerns regarding observations during the course of this trial. The DMID Medical Monitor is empowered to stop study enrollment and study product administration if adverse events that meet the halting criteria are reported. The DMID Medical Monitor and the ISM will be responsible for reviewing SAEs in real time. The DSMB will review SAEs on a regular basis and ad hoc during this trial.

#### Independent Safety Monitor (ISM)

ISMs are physicians with relevant pediatric expertise and whose primary responsibility is to provide timely independent safety monitoring. The ISM (one for each site) will not be directly involved in the trial, will not be under the investigators' supervision, and will have no financial, intellectual, proprietary or professional interest in the outcome of the trial. An ISM with relevant sinusitis and/or pediatric infectious diseases expertise is assigned to each participating clinical study site, is in close proximity to the site and has the authority to readily access study participant records. The ISM reviews any SAE in real time and other AEs as needed and provides an independent assessment to the investigators and DMID. The ISM will not contact the DSMB directly.

## **10 CLINICAL MONITORING**

### **10.1 Site Monitoring Plan**

Site monitoring will be conducted to ensure that human subject protections, study procedures, laboratory procedures, study intervention administration, and data collection processes are of high quality and meet DMID, University of Pittsburgh, and ICH E6 (GCP) guidelines and applicable regulations, and that this trial is conducted in accordance with the protocol, protocol-specific MOP, and applicable standard operating procedures.

Independent clinical study site monitoring will be conducted as detailed in the clinical monitoring plan. This will include on-site monitoring visits at standard intervals, or more frequently as necessary, throughout the study to oversee data collection, review source documentation, ensure GCP, protocol and regulatory compliance, and resolve data queries. Monitoring visits will include, but are not limited to review of regulatory files, accountability records, eCRFs, informed consent forms, medical and laboratory reports, and protocol compliance. The monitor's Clinical Research Associates (CRAs) will have reasonable access to the participating clinical study sites, study personnel, and all study documentation. CRAs will meet with participating clinical study site investigators to discuss any problems and actions to be taken and document visit finding and discussions. Clinical monitoring reports will be submitted to the principal investigators and DMID.

## 11 STATISTICAL CONSIDERATIONS

### 11.1 Study Hypotheses

Hypothesis 1: Children not colonized with respiratory pathogens are unlikely to benefit from antimicrobial therapy.

Hypothesis 2: Children without colored nasal discharge are unlikely to benefit from antimicrobial therapy.

### 11.2 Primary and Secondary Analyses

#### Primary

- To determine whether the effect of antimicrobial treatment differs in predefined subgroups of children with acute sinusitis (i.e., to test for treatment subgroup interactions). Subgroups will be defined by the (1) presence vs. absence of nasopharyngeal (NP) colonization with respiratory pathogens (*Streptococcus pneumoniae*, *Haemophilus influenzae*, or *Moraxella catarrhalis*), and (2) presence vs. absence of colored (yellow or green) nasal discharge.

#### Secondary

- To determine whether antimicrobial therapy is superior to placebo (i.e., to test for the overall effect)

#### Tertiary

- To evaluate compliance with study product
- To assess adverse events associated with use of amoxicillin clavulanate, including the development of bacterial resistance
- To compare resource utilization according to treatment strategy

### 11.3 Analysis Populations

#### 11.3.1 Intent-to-Treat Population (ITT)

The ITT population will consist of all eligible randomized children with at least 1 diary entry. This population will form the basis for the primary and secondary efficacy analyses of study data as well as for the safety analyses.

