### **5.3.2 Reasons for Withdrawal**

The following events are to be considered sufficient reason for discontinuation of a subject from the study product:

- Parents/legal guardians request; subjects are free to withdraw from participating in the study at any time upon request.
- Parents/legal guardians who do fail to complete any of the diaries during the first 4 days of the study will be withdrawn for non-compliance.

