### **5.3.3 Handling of Withdrawals**

If a parent/legal guardian is unwilling to continue follow-up through scheduled study visits, the subject will be referred back to their primary care provider (PCP) for continued antibiotic treatment and follow-up. Subjects withdrawn due to non-compliance will be replaced.

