## **6.6 Concomitant Medications/Treatments**

Medication history will be obtained by interview of the parents/legal guardians. We will ask about previous antihistamines, decongestant, albuterol, or corticosteroid use during the past 7 days and antibiotics use up to 3 months before enrollment.

Use of select oral or nasal concomitant medications (antihistamines, decongestants, albuterol, antibiotics, corticosteroids, and analgesics) taken by the subject from the time of consent through the end-of-study follow-up visit or early termination, whichever occurs first, will be ascertained by parent/legal guardian interview at the end-of-study follow-up visit or early termination, whichever occurs first. Receipt of a systemic antibiotic while taking study medication will be recorded as this constitutes a secondary endpoint of the study.

Medications that might interfere with the evaluation of the investigational product should not be used unless absolutely necessary. Medications in this category include: systemic corticosteroids, nasally administered decongestants or corticosteroids, and systemic medications containing decongestants, antihistamines, or corticosteroids. During participation in this study, subjects should not participate in any other clinical trial and should not receive any investigational drug or vaccine. The use of ibuprofen and acetaminophen is permitted. In the event of an allergic reaction to the assigned study product, subjects will be treated with clindamycin plus cefixime, or levofloxacin or a similar antibiotic, as clinically indicated using the results of the NP culture to guide therapy and without breaking the blind.

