### 11.6.3 Subject Disposition

The number of patients screened, randomized, withdrawn, and included in each analysis population (ITT, Per Protocol) will be reported by treatment group and according to site. In addition, the number of patients completing this trial and the reasons for patient withdrawal will be tabulated by treatment group. These data will be used to prepare a CONSORT diagram.

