### **11.7.3 Secondary Efficacy Analyses of the Secondary Endpoints**

Secondary efficacy variables include treatment failure, development of AOM, and receipt of an antibiotic. All of these are dichotomous variables. We will use the Cochran-Mantel-Haenszel test stratified by study site, using the ITT dataset.

Additional analyses of the dichotomous secondary efficacy variables will use logistic regression to adjust for baseline covariates and other prognostic variables.

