## **11.9 Handling of Data from Withdrawn Subjects**

All such subjects who have at least 1 diary entry will be included in the intent-to-treat analysis population.

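### The safety analyses and the antibiotic-receipt endpoint use a set that requires a diary entry, so a dosed child without one drops out of the compared incidences; no all-treated set is defined

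*Combined protocol and SAP*

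**What the plan says.** Section 11.3.1: "The ITT population will consist of all eligible randomized children with at least 1 diary entry". The same section gives this set its uses: "This population will form the basis for the primary and secondary efficacy analyses of study data as well as for the safety analyses". Section 11.3.2 adds a Per Protocol set based on 70% of doses. Section 11.6.3 confirms that there are only two, since it tabulates the numbers "included in each analysis population (ITT, Per Protocol) will be reported by treatment group and according to site".

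Section 11.7.3 tests treatment failure, acute otitis media (AOM) and antibiotic receipt by a Cochran-Mantel-Haenszel test "stratified by study site, using the ITT dataset". Section 11.10.2 tabulates adverse events by arm, and compares serious events and discontinuations due to adverse events by Fisher's exact test. It names no other population.

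On children with poor diary completion, section 5.3.2 says: "Parents/legal guardians who do fail to complete any of the diaries during the first 4 days of the study will be withdrawn for non-compliance". Section 5.3.3 continues: "Subjects withdrawn due to non-compliance will be replaced". Section 11.9 says of withdrawn children: "All such subjects who have at least 1 diary entry will be included in the intent-to-treat analysis population". Section 11.8 excludes children who have no diary entry at all, then gives a worst-case and best-case sensitivity analysis for patients with a missing binary outcome.

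**The concern.** Having a diary entry is a post-randomization behavior. Using it to define the safety set means that a child who received study product can be absent from the compared incidences and their denominators. An early adverse event is one conceivable reason why a family never starts the diary, so the exclusion need not be unrelated to the outcome.

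For antibiotic receipt the condition also serves no purpose. Section 6.6 has this use "ascertained by parent/legal guardian interview at the end-of-study follow-up visit or early termination, whichever occurs first", so the outcome may be known for a child whom the analysis discards. The result would still carry the ITT label. Table 2 of the protocol counts departure from the intention-to-treat principle as a limitation of an earlier trial and adherence to it as a feature of this one.

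**Working it through.** **Can a dosed child have no diary entry?**

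1. Section 7.2 gives the first dose at enrollment after randomization, when possible, and adverse event monitoring starts then. The diary is an evening task (7.3).
2. The entry made at the enrollment visit is a practice entry (section 4), and section 8.1 treats Day 1 recording as optional. Enrollment therefore does not guarantee an entry, and section 11.8 itself provides for children with none.
3. Under section 6.2, a child enrolled before 1 PM who follows the schedule has 2 doses on Day 1 and 2 + 3 × 2 = 8 by the end of Day 4. One enrolled after 1 PM has 1 and 1 + 3 × 2 = 7. The full course is 10 × 2 = 20 doses, so exposure before withdrawal can be substantial.
4. Section 5.3.2 can mean that no early diary was completed, or that any one was missed. The reading does not matter here: sections 11.3.1 and 11.8 exclude the child with no entry either way, and section 11.9 keeps a withdrawn child who has one.
5. Per Protocol does not bring these children back, because compliance is itself assessed from the diary (11.10.1).

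**Which outcomes can exist without a diary?**

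| Outcome | Source | Diary needed? |
|---|---|---|
| Adverse events other than diarrhea | Recorded from first study intervention to final visit (9.1); asked about at the final visit (7.4) | No |
| Protocol-defined diarrhea | Tracked in the diary (11.10.2) | Largely |
| Antibiotic receipt | Parent interview (6.6, 8.1) | No |
| AOM | Symptoms plus a bulging tympanic membrane (11.4.2) | No, but needs an examination |
| Treatment failure | Criteria b to d, and mostly a, use diary scores (11.4.2) | Mostly |

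**How many children?** The documents give no rate of children without any entry. Let z be an assumed share.

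- 688 randomized: 688z = 3.4, 6.9, 13.8 for z = 0.5%, 1%, 2%; per arm of 344, 1.7, 3.4, 6.9.
- Replacement until 688 are analyzed: 688/(1 − z) = 691.5, 694.9, 702.0 randomized, so 3.5, 6.9, 14.0 fall outside the tables.
- Outer case: the preliminary study's retention was 94%. Retention is not the same as having a diary entry, but z = 6% gives 688/0.94 = 732 randomized and 44 left out.

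**Effect on an incidence.** With k events among 343 counted children, adding one omitted child who had the event changes the incidence by (k + 1)/344 − k/343 = (343 − k)/(344 × 343). The maximum is at k = 0: 1/344 = 0.29 percentage points. Adding an event-free child changes it by at most the same amount.

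**Effect on a binary endpoint.** If the rate among counted children is p, the rate over all randomized lies between p(1 − z) and p(1 − z) + z. The width is z whatever p is, so this restates the assumed share and is no independent evidence of size. The documents give no expected rate of antibiotic receipt, so no band is worked for it.

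**The case against.** The strongest reply is that almost no child will be affected. A single entry suffices. Families not reachable by phone are excluded (Table 3), devices are loaned, entries are paid for, and a missing score is pursued every morning (sections 4 and 7.3). A family that ignores all of this may not give a closing interview either, so some of the adverse event and antibiotic data may not exist. This stands. It limits the size of the problem, and it is why a wider safety set must report the number assessed, so that a child with no follow-up is not counted as event-free.

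A second reply is that the safeguards lie elsewhere. Individual reporting of serious events (9.3.1), the halting rules (9.5), real-time review by the safety monitors (9.6) and the narratives (11.10.2) carry no diary condition. The disposition table would show exclusions by arm and site, and section 11.8 compares missing-data proportions between arms. This also stands. A reader might infer that serious events could go unseen; the documents do not support that. What remains is the compared incidences and their denominators.

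A reader might also infer that AOM is known from the interview in the same way as antibiotic receipt. It is not: section 6.6 covers medications, while AOM needs an ear examination. Section 7.4 asks about visits to other providers and section 15.2 allows outside records, so AOM may sometimes be recovered, but for a child without a diary it would probably be imputed, as treatment failure would be.

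Nor do the documents show that exclusion differs by arm. Section 9.2.4 asks children who stop product to keep recording symptoms, and the link from an early event to an unstarted diary is only a possibility. Replacement by itself removes nobody from the analysis; the diary condition does.

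**Conclusion.** The point holds for the compared adverse event incidences and for antibiotic receipt. The plan states a rule that drops exposed children for a post-randomization reason, and defines no all-treated set. The word eligible in the ITT definition opens a second route out, for dosed children later found ineligible.

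Section 11.8 does not clearly close the gap. Its exclusion sentence follows the text on the primary endpoint and its sensitivity rule then speaks of patients generally, but section 11.7.3 confines the binary analyses to the ITT dataset. Two statisticians could read it differently.

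The effect is probably small: about 3 to 14 children at assumed shares of 0.5% to 2%, and at most 0.29 points per omitted child in an arm of 344. These shares are assumptions. The primary PRSS analysis by generalized estimating equations (GEE) is not affected, and nothing here shows that any result would change. Confidence is high on what the text says and low on the number affected. It is a cheap improvement worth making before unblinding.

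**What to change.** 1. Define a safety set of all randomized children who received at least one dose, by treatment received, regardless of diary entry, later-found ineligibility or replacement. Report the number assessed for each type of adverse event, diary-derived diarrhea in particular. List this set in section 11.6.3.
2. Analyze antibiotic receipt in all randomized children with the outcome ascertained.
3. State in section 11.8 that the worst/best-case analysis for all three binary endpoints covers randomized children without a diary, and note that AOM and treatment failure will be largely imputed for them.
4. Keep the diary condition for the PRSS GEE model only.

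The cost is SAP wording, one more analysis set and one reporting rule. No extra children or data collection are needed. The downside is a few more children with imputed or unknown outcomes.
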